3.4 Primary Safety Endpoints

N/A

4 Subject Selection and Withdrawal

4.1 Inclusion Criteria

- 1. Age 50 and older
- 2. Meet criteria for either a) amnestic mild cognitive impairment (single or mixed domain) or Alzheimer's disease, or b) have no cognitive impairment, based on history, exam, and neuropsychological testing.
- 3. Subjects unable to provide informed consent must have a surrogate decision maker
- 4. Written and oral fluency in English
- 5. Able to participate in all scheduled evaluations and to complete all required tests and procedures.
- 6. In the opinion of the investigator, the subject must be considered likely to comply with the study protocol and to have a high probability of completing the study.

4.2 Exclusion Criteria

- 1. Past or present history of certain brain disorders other than MCI or AD.
- 2. Certain significant medical conditions, which make study procedures of the current study unsafe. Such serious medical conditions include uncontrolled epilepsy and multiple serious injuries.
- 3. Contraindication to MRI scanning
- 4. Conditions precluding entry into the scanners (e.g. morbid obesity, claustrophobia, etc.).
- 5. Exposure to research related radiation in the past year that, when combined with this study, would place subjects above the allowable limits.
- 6. Participation in the last year in a clinical trial for a disease modifying drug for AD.
- 7. Inability to have a catheter in subject's vein for the injection of radioligand.
- 8. Inability to have blood drawn from subject's veins.
- 9. Taking anticoagulant medication (e.g., warfarin).

4.3 Subject Recruitment and Screening

Men and women age 50 and older will be recruited from the Columbia Doctors Aging and Dementia clinic, the CUMC Alzheimer's Disease Research Center (ADRC), [name] Questionable Dementia 2 (QD2) cohort, and the CUMC Washington Heights-Inwood Community Aging Project (known locally as WHICAP, R01 AG037212, PI [name]). Participants may also co-enroll from the cognitive aging studies of [name] (protocol AAAO9758) and [name] (protocols AAAI2752, AAAQ8249, and

AAAQ8096), and from CUMC protocols AAAO1151, AAAQ7868, and AAAR4352 (PI = [name]). Participants may also self-refer as this study will be registered on clinicaltrials.gov.

Informed consent will be obtained by a qualified investigator prior to study enrollment. Subjects will undergo screening including history, physical examination, routine laboratory studies, neuropsychological testing, brain MRI, and amyloid PET imaging to identify cohorts who are amyloid-positive with impairment (target n = 15) or amyloid-negative with normal cognition (n = 15). Approximately 40% of screened subjects are expected to fail screening procedures or withdraw from the study. We therefore plan to screen 50 subjects to ensure a total of 30 completers. Subjects who are co-enrolled in other CUMC studies will not need to have brain MRI or screening laboratories under this protocol if done within the last 12 months. Coenrolled subjects will not need to have ¹⁸F-florbetaben PET under this protocol if 1) they are controls and have had a negative ¹⁸F-florbetaben or other amyloid PET scan within the previous 12 months, or 2) they are patients and have ever had a positive amyloid PET scan using any amyloid radioligand (¹⁸F-florbetaben, ¹⁸F-florbetapir, ¹⁸F-flutemetamol, or ¹¹C-Pittsburgh Compound B).

During screening, participants will be administered a neuropsychological test battery and a medical interview.

If any of the above screening procedures have been performed within one year of the ¹¹C-ER176 PET scan visit, then those procedures will not need to be repeated under this protocol. Rather the previously obtained results will be used.

The diagnosis of MCI or AD will be based on updated criteria[25, 26]. The neuropsychological test battery will include the following tests: the Mini-Mental State Examination, Selective Reminding Test, Benson Complex Figure Copy and Recall, MINT, Rosen Drawing Test, single word and sentence repetition from the NACC FTD module, Geriatric Depression Scale (15 items), Trail Making Tests A and B, and Verbal Fluency (CFL, and Animals). Raw scores and demographically corrected T-scores (age, years of education, sex, and ethnicity) will be determined.

Subjects will be categorized by cognitive status, as impaired or unimpaired, based on a) history of cognitive impairment, b) neurological exam, c) neuropsychological testing, and d) a study team consensus diagnosis.

4.4 Early Withdrawal of Subjects

4.4.1 When and How to Withdraw Subjects

Subjects will be withdrawn if they develop serious medical illness during the study, defined as an event determined to be grade 3 or higher, i.e., severe or life-threatening. The exception is a single event of syncope if felt by the PI to be vasovagal in etiology and related to catheter placement or venipuncture. Vasovagal syncope in response to blood drawing and IV placement is common and does not warrant study withdrawal if the subject's loss of consciousness is brief (i.e., less than 5 minutes) and does not require further medical attention.

4.4.2 Data Collection and Follow-up for Withdrawn Subjects

Data collected prior to withdrawal will be analyzed if possible. No data collection will take place after withdrawal in subjects who drop out of the study.

5 Study Drug

5.1 Description

- 5.1.1. ¹¹C-ER176 is a PET radioligand that binds to the 18 kDa translocator protein. ¹¹C-ER176 will be administered at tracer doses and is not expected to have a pharmacological effect.
- 5.1.2. ¹⁸F-Florbeteben is a PET radioligand that binds to amyloid plaques. ¹⁸F-Florbetaben will be administered at tracer doses and is not expected to have a pharmacological effect.

5.2 Treatment Regimen

N/A

5.3 Method for Assigning Subjects to Treatment Groups

N/A

5.4 Preparation and Administration of Study Drug

¹¹C-ER176 will be synthesized and administered by the CUMC PET Department. Injection will be administered at a target imaging dose of up to 20 mCi (740 MBq).

¹⁸F-florbetaben will be synthesized by an off-site commercial manufacturer and delivered to the CUMC PET Department as a clear solution containing ¹⁸F-florbeteben (drug substance) formulated for intravenous bolus administration. 18F-florbetaben injection will be administered at a target imaging dose of up to 8.1 mCi (300 MBq).

Calculation of activity to be injected will be performed by a qualified radiopharmacist in the CUMC PET department.

5.5 Subject Compliance Monitoring

N/A

5.6 Prior and Concomitant Therapy

Subjects will not be included in the study if they have participated in the last year in a clinical trial for a disease modifying drug for AD.

5.7 Packaging

N/A

5.8 Blinding of Study Drug

N/A

5.9 Receiving, Storage, Dispensing and Return

5.9.1 Receipt of Drug Supplies

Upon receipt of the of the study treatment supplies, the CUMC PET Center staff will perform an inventory and a drug receipt log will be filled out and signed by the person accepting the shipment. Any damaged or unusable study drug in a given shipment (active drug or comparator) will be documented in the study files.

5.9.2 Storage

N/A

5.9.3 Dispensing of Study Drug

Both ¹¹C-ER176 and ¹⁸F-florbetaben will be administered the same day of synthesis or delivery to the CUMC PET Department.

5.9.4 Return or Destruction of Study Drug

Any unused radiopharmaceutical will be on site and documented in the study files.

6 Study Procedures

This study will involve up to 5 outpatient visits. See schedule below.

At the first screening visit, subjects will sign informed consent, undergo history and physical and neurological examination, neuropsychological testing, and have blood drawn and urine collected for routine safety laboratories and TSPO genotyping. Subjects who have previously had TSPO genotyping will not need to repeat this blood test regardless of when they were last genotyped for TSPO. Additional screening visits are required for brain MRI and ¹⁸F-florbetaben PET scan. Flexibility is allowed in screening procedures such that procedures may be performed in any order and may be performed on the same day if schedule allows for subject convenience. Subjects who already had brain MRI or safety laboratories performed under a different CUMC protocol do not need to have them repeated unless performed more than 12 months prior to inclusion in this study. Coenrolled subjects will not need to have ¹⁸F-florbetaben PET under this protocol if 1) they are controls and have had a negative ¹⁸F-florbetaben PET scan within the previous 12 months, or 2) they are patients and have ever had a positive amyloid PET scan using any amyloid radioligand (¹⁸F-florbetaben, ¹⁸F-florbetapir, ¹⁸F-flutemetamol, or ¹¹C-Pittsburgh Compound B).

Up to 3 screening visits are anticipated. However, additional visits may be necessary if certain tests must be scheduled on different days due to scheduling.

Screening procedures may be performed in any order and may be performed on the same day as the ¹¹C-ER176 PET scan if schedule allows for subject convenience. Subjects who already had brain MRI or safety laboratories performed under a different CUMC protocol do not need to have them repeated unless performed more than 12 months prior to inclusion in this study. If any of the above screening procedures have been performed within one year of the ¹¹C-ER176 PET scan visit, then those procedures will not need to be repeated under this protocol. Rather the previously obtained results will be used. The ¹¹C-ER176 PET scan will be performed on a different day after screening procedures are completed. For the 4 subjects having test-retest imaging, two ¹¹C-ER176 PET scans will be performed. These may be performed on the same day or on separate days.

Subjects will have a total of 70 mL of venous blood drawn at time of screening to be used for screening laboratories, *TSPO* genotyping, and other research tests. Blood samples will be stored prior to research use in a secure freezer. Stored samples will be labeled with subject ID number and no personal identifying information will be included on the stored sample label. Results will not be released to participants.

Study Schedule

	Screen ^a	Study ^b	
Study Procedures	≤12 months	Visit 1 (within 12 months of first screening visit)	Visit 2 (within 12 months of first screening visit)
Informed consent	X		
Medical/psychiatric history	X		
Inclusion/exclusion criteria	X		
Blood draw	X		
Neuropsychological testing	X		
MRI	X		
¹⁸ F-florbetaben PET scan	X		
¹¹ C-ER176 PET		X	X c
Laboratory determinations ^d	X		
Neurological examination	X		
Vital signs	X	_	
Height and weight	X	X	
Adverse events ^e	X	X	X

- a. Screening procedures may be performed in any order and may be performed on the same day if schedule allows for subject convenience Subjects who already had brain MRI or safety laboratories performed under a different CUMC protocol do not need to have them repeated unless performed more than 12 months prior to inclusion in this study. If any of the above screening procedures have been performed within one year of the ¹¹C-ER176 PET scan visit, then those procedures will not need to be repeated under this protocol. Rather the previously obtained results will be used. Coenrolled subjects will not need to have ¹⁸F-florbetaben PET under this protocol if 1) they are controls and have had a negative ¹⁸F-florbetaben or other amyloid PET scan within the previous 12 months, or 2) they are patients and have ever had a positive amyloid PET scan using any amyloid radioligand (¹⁸F-florbetaben, ¹⁸F-florbetapir, ¹⁸F-flutemetamol, or ¹¹C-Pittsburgh Compound B). Up to 3 screening visits are anticipated. However, additional visits may be necessary if certain tests must be scheduled on different days due to scheduling.
- b. Study procedures must be completed within 12 months of MRI. Screening procedures may be performed on the same day as the ¹¹C-ER176 PET scan for subject convenience if schedule allows.
- c. Four controls subjects will undergo 2 ¹¹C-ER176 PET scans, which may be performed on the same day or on different days.
- d. Laboratory determinations here include complete blood count, basic metabolic panel, liver functions tests, thyroid stimulating hormone, and urinalysis.

e. Adverse event reporting on Visit 2 to be performed after the ¹¹C-ER176 PET scan is completed. Subject will be called by telephone 24 hours after both the ¹⁸F-florbetaben and ¹¹C-ER176 PET scans for follow up adverse event reporting. Follow up adverse event reporting for ¹⁸F-florbetaben is not needed if the amyloid PET scan is performed under a separate protocol.

7 Statistical Plan

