1.3.2. Preclinical Data for ¹⁸F-florbetaben

1.3.2.1. Pharmacology of ¹⁸F-florbetaben

 18 F-florbetaben is a 18 F-labeled stilbene derivative, which binds to β-amyloid plaques in the brain. The F-18 isotope produces a positron signal that is detected by a PET scanner. 3H florbetaben in vitro binding experiments reveal two binding sites (Kd of 16 nM and 135 nM) in frontal cortex homogenates from patients with AD. Binding of 18 F-florbetaben to β-amyloid plaques in post-mortem brain sections from patients with AD using autoradiography correlates with both immunohistochemical and Bielschowsky silver stains. 18 F-florbetaben does not bind to tau or α-synuclein in tissue from patients with AD. Neither Neuraceq nor non-radioactive florbetaben F-18 bind to AT8 positive tau deposits in brain tissue from patients with frontotemporal dementia (FTD), using autoradiography and immunohistochemistry, respectively.

Following intravenous administration, ¹⁸F-florbetaben crosses the blood brain barrier and shows differential retention in brain regions that contain β-amyloid deposits. Differences in

signal intensity between brain regions showing specific and nonspecific ¹⁸F-florbetaben uptake form the basis for the image interpretation method.

Results from the first in-human study of ¹⁸F-florbetaben are as follows (see Package Insert). Ten minutes after intravenous bolus injection of 300 MBq of 18F-florbetaben in human volunteers, approximately 6% of the injected radioactivity was distributed to the brain. 18F-florbetaben plasma concentrations declined by approximately 75% at 20 minutes post injection, and by approximately 90% at 50 minutes. The F-18 in circulation during the 45- 130 minute imaging window was principally associated with polar metabolites of florbetaben. ¹⁸F-florbetaben was 8.5% bound to plasma proteins and was eliminated from plasma primarily via the hepatobiliary route with a mean biological half-life of approximately 1 hour. In vitro studies show that metabolism of florbetaben is predominantly catalyzed by CYP2J2 and CYP4F2. At 12 hours post-administration, approximately 30% of the injected radioactivity had been excreted in urine. Almost all F-18 radioactivity in urine was excreted as polar metabolites of ¹⁸F-florbetaben and only trace amounts of ¹⁸F-florbetaben were detected. In in vitro studies using human liver microsomes, florbetaben did not inhibit cytochrome P450 enzymes at concentrations present in vivo.

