3.1 General Design

3.1.1. Subject recruitment and screening procedures

Men and women age 50 and older will be recruited from the Columbia Doctors Aging and Dementia clinic, the CUMC Alzheimer's Disease Research Center (ADRC), [name] Questionable Dementia 2 (QD2) cohort, and the CUMC Washington Heights-

Inwood Community Aging Project (known locally as WHICAP, R01 AG037212, PI [name]). Participants may also co-enroll from the cognitive aging studies of [name] (protocol AAAO9758) and [name] (protocols AAAI2752, AAAQ8249, and AAAQ8096), and from CUMC protocols AAAO1151, AAAQ7868, and AAAR4352 (PI = [name]). Participants may also self-refer as this study will be registered on clinicaltrials.gov. Informed consent will be obtained prior to study enrollment.

For subjects with cognitive impairment, prior to obtaining informed consent, a licensed physician who is not listed as personnel on this protocol will determine whether the subjects has capacity to provide their own consent. If the subject lacks consent, a legally authorized representative will be required to provide consent for the subject. Only subjects who can provide an understanding of the study procedures, particularly of the risk of pain associated with the arterial catheter placement, by providing verbal assent, may be enrolled via the surrogate consent process. Subjects who are unable to provide meaningful assent will not be enrolled into the study.

Up to 50 subjects will undergo screening including history, physical examination, routine laboratory studies, neuropsychological testing, brain MRI, and amyloid PET imaging.

If any of the above screening procedures have been performed within one year of the ¹¹C-ER176 PET scan visit, then those procedures will not need to be repeated under this protocol. Rather the previously obtained results will be used.

Subjects will be categorized as either amyloid-positive or amyloid-negative on PET. Subjects will be identified as either cognitively normal or cognitively impaired in consensus conference. Subjects must have Clinical Dementia Rating scale score of 0.5 or above and meet clinical criteria for either amnestic MCI (single or multiple-domain)[25] or Alzheimer's disease[26] to be included in the cognitively impaired category. Of the screened subjects, only amyloid-positive patients and amyloid-negative controls will undergo ¹¹C-ER176 PET.

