Subjects will have genetic analysis to determine the presence of the rs6971 (Ala147Thr) SNP on the TSPO gene.

Target sample size for completers is 15 amyloid-positive patients and 15 amyloid-negative controls (30 subjects total). Our enrollment goal of 25 subjects per group will allow a 40% general screen failure/drop-out rate. Subjects who are coenrolled in other CUMC studies will not need to have brain MRI under this protocol if done within the last 12 months. Coenrolled subjects will not need to have ¹⁸F-florbetaben PET under this protocol if 1) they are controls and have had a negative ¹⁸F-florbetaben or other amyloid PET scan within the previous 12 months, or 2) they are patients and have ever had a positive amyloid PET scan using any amyloid radioligand (¹⁸F-florbetaben, ¹⁸F-florbetapir, ¹⁸F-flutemetamol, or ¹¹C-Pittsburgh Compound B).

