3.1.3. Imaging procedures

One brain MRI will be performed on each subject using a 3T scanner. Sequences performed will include 3D T1 (MPRAGE, 180 slice 1 mm resolution, 256 x 256 voxel count) for volumetric analysis and clinical sequences to exclude subjects with other intracranial pathology unrelated to AD. PET scans will take place on a Biograph mCT PET scanner (Siemens Healthcare) at the CUMC Kreitchman PET Center. Subjects will have one ¹⁸F-florbetaben (Neuraceq) PET scan (up to 8.1 mCi) to determine amyloid status[27]. Subjects will have one PET scan with ¹¹C-ER176 (injected activity 10-20 mCi), except for 4 controls who will have two ¹¹C-ER176 scans for test-retest imaging. ¹¹C-ER176 imaging will be performed with arterial sampling. ¹¹C-ER176 will be synthesized by the CUMC PET Department Radiochemistry Laboratory. ¹⁸F-Florbetaben will be purchased from Piramal Imaging. Subjects will be informed if a clinically important abnormality is detected on PET imaging (e.g., brain tumor).

Prior to 11 C-ER176 PET imaging, one arterial catheter and one intravenous catheter will be placed. After a low-dose CT scan for attenuation correction, up to 20 mCi 11 C-ER176 will be injected intravenously over 3 minutes. Emission scan will begin at the start of the radioligand infusion according to the following frame schedule: 30 seconds x 6, 1 minute x 3, 2 minutes x 2, and 5 minutes x 16 for total scan time of 90 min. During the emission scan, arterial samples will be drawn at 10 second intervals for the first 4 min using an automated blood sampler. Thereafter, manual arterial samples will be drawn at 6, 8, 10, 15, 20, 30, 40, 50, 60, 75, and 90 minutes. Alternatively, manually samples may be drawn at 15 sec intervals for the first 2.5 min, then at 3, 4, 6, 8, 10, 15, 20, 30, 40, 50, 60, 75, and 90 minutes. Radioactivity in plasma will be quantified by a γ -counter and analyzed by reverse-phase chromatography to separate parent radioligand from radiometabolites[43] by the PET center radiometabolite laboratory. Free fraction of 11 C-PBR28 in plasma (f_P) will be measured by ultrafiltration and normalized using a standard derived from pooled donor plasma[44]. Because one aim is to determine if 11 C-ER176 may be useful in AD studies using simplified analysis, some subjects may have 11 C-ER176 imaging without arterial catheterization .

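### The plan both permits and rules out 18F-florbetaben on the day of the 11C-ER176 scan, and has no safeguard against residual F-18 entering the primary PET measures

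*Combined protocol and SAP*

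**What the plan says.** **Same-day permission.** Study Schedule footnote b (section 6) states: "Screening procedures may be performed on the same day as the ¹¹C-ER176 PET scan for subject convenience if schedule allows". The text of section 6 gives the same permission. Neither place excepts florbetaben or sets an interval between tracers.

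**Opposing statement.** The same paragraph of section 6 says: "The ¹¹C-ER176 PET scan will be performed on a different day after screening procedures are completed".

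**Florbetaben PET counts as screening.** The schedule table marks it in the Screen column, and section 3.1.1 includes it: "Up to 50 subjects will undergo screening including history, physical examination, routine laboratory studies, neuropsychological testing, brain MRI, and amyloid PET imaging".

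**Amyloid status decides who is scanned.** Section 3.1.1: "Of the screened subjects, only amyloid-positive patients and amyloid-negative controls will undergo ¹¹C-ER176 PET". Co-enrolled patients need no new amyloid scan if "they are patients and have ever had a positive amyloid PET scan using any amyloid radioligand". Co-enrolled controls are exempt only if they had a negative scan in the previous 12 months.

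**Measurement.** Section 3.1.3 sets a 90-minute ER176 scan with 10-20 mCi injected, gamma counting of plasma, and chromatography to separate parent from radiometabolites. Sections 3.2 and 7.2 define the outcome as regional effect sizes for V_T/f_P and for SUVR on the cerebellum. None of these sections mentions an F-18 background scan, blank or correction.

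**The concern.** Staff could follow either scheduling statement. If they follow the permission for a subject who needs a new florbetaben scan, florbetaben is injected first and ER176 some hours later. Both isotopes are positron emitters, and neither the scanner nor a gamma counter that registers total activity tells them apart. F-18 decays more than five times more slowly than C-11 (109.8/20.4 = 5.4). Counts corrected for C-11 decay would therefore give leftover F-18 a weight that grows through the ER176 scan.

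The contamination would not be neutral between groups. Section 1.3.2.1 says florbetaben is retained differentially in regions containing amyloid. By design all scanned patients are amyloid-positive and all scanned controls amyloid-negative. Residual florbetaben could therefore enter one of the two primary measures, cortex/cerebellum SUVR, in a way that depends on group. The same section attributes circulating F-18 during the florbetaben imaging window mainly to polar metabolites, so plasma counts behind V_T/f_P could be affected too.

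**Working it through.** **Inputs from the protocol**
- Florbetaben: up to 8.1 mCi; 8.1 × 37 = 299.7, so 300 MBq as stated (section 5.4).
- ER176: 10-20 mCi, i.e. 370-740 MBq (section 3.1.3).
- ER176 scan length, recomputed from the frames: 6×0.5 + 3×1 + 2×2 + 16×5 = 90 min, as stated.
- Florbetaben brain uptake at 10 min: about 6% of injected activity (section 1.3.2.1).
- ER176 brain SUV at 60-120 min: 1.3, 1.0 and 0.8 in high-, mixed- and low-affinity binders (Table 1, section 1.4.1.2).

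**Assumptions not in the protocol**
- Half-lives of 109.8 min (F-18) and 20.4 min (C-11).
- Gap T between injections. The florbetaben image is acquired at 50-70 min and then read (section 3.1.4), so a gap of a few hours is physically possible.
- A late ER176 window of 60-90 min for SUVR. The plan does not specify one.
- 5-30% of the 10-min florbetaben uptake still in the brain, held constant over T.
- A florbetaben cortex:cerebellum ratio 0.2-0.6 higher in amyloid-positive than in amyloid-negative subjects.
- An SUVR SD of 0.10.
- Whole-brain ER176 SUV standing in for cerebellum.

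**Step 1: physical decay, whole body**

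F-18 at 75 min into the ER176 scan = 300 × 2^(−(T+75)/109.8). C-11 at the same time = A × 2^(−75/20.4).
- T = 180 min: 300 × 2^(−255/109.8) = 60 MBq F-18.
- T = 360 min: 300 × 2^(−435/109.8) = 19 MBq F-18.
- T = 1,440 min: 0.034 MBq is left when ER176 is injected.
- C-11: 58 MBq for A = 740 and 29 MBq for A = 370.

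These figures ignore excretion and are not brain signals.

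**Step 2: illustrative brain signal**

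The 6% uptake in an assumed 1.4 kg brain and 70 kg body is an SUV of 0.06 × 70/1.4 = 3.0. Retention of 5-30% leaves 0.15-0.90. The apparent SUV of residual F-18 is that value × (300/A) × 2^(−(T+t)/109.8) × 2^(t/20.4), averaged over t = 60-90 min. Its share of the signal is f = apparent F-18 SUV / (apparent F-18 SUV + ER176 SUV).

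**Step 3: effect on SUVR**

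The observed ratio is (1−f) × ER176 ratio + f × florbetaben ratio. If both groups are exposed with the same f and have the same true ER176 ratio, the false difference is f × (florbetaben ratio in positives − ratio in negatives). Dividing by the SD gives the false effect size.

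Results for 740 MBq ER176. The share covers all genotypes and 5-30% retention. The SUVR difference is for mixed-affinity binders. The effect size takes 10% retention and assumes every subject is scanned same-day.

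| Gap | F-18 share of late brain signal | False SUVR difference | False effect size |
|---|---|---|---|
| 3 h | 11-55% | 0.03-0.29 | 0.48-1.45 |
| 6 h | 4-28% | 0.01-0.14 | 0.19-0.56 |
| 8 h | 2-15% | 0.005-0.08 | 0.09-0.28 |
| 12 h | 0.4-4% | 0.001-0.02 | 0.02-0.06 |
| 24 h | under 0.05% | at most 0.0002 | about 0 |

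At 370 MBq the apparent F-18 SUV doubles. The 24 h figures remain negligible (share at most 0.08%, false difference at most 0.0004).

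**Step 4: unequal exposure**

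If only controls were scanned same-day, their mean would shift by f × (florbetaben ratio in amyloid-negatives − ER176 ratio). The protocol gives neither ratio, so the sign is unknown. An upward shift in controls would shrink an apparent increase in AD.

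**The case against.** The strongest reply is that the problem disappears if the different-day sentence governs, as the 24 h row shows. That is correct, and it is why this point is a contradiction to be reconciled. A reader of footnote b alone might infer that same-day florbetaben is settled policy. The documents do not support that, and they do not show that any subject would receive both tracers on one day.

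The requirement to know amyloid status also works against a short gap. The florbetaben image needs a blinded visual read, cognitive status is settled in a consensus conference, and an arterial line is usually placed before ER176. Section 6 says further screening visits are needed for MRI and florbetaben PET, and the permission applies only where scheduling allows. All this makes a 3 h gap less likely, but nothing excludes it or a longer same-day gap.

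A reader might also infer that carry-over would imitate the primary result. That does not follow. Patients are exempt after any earlier positive scan, controls only after a negative scan within 12 months, so new florbetaben scans could be more common in controls. For V_T/f_P, F-18 could enter both the tissue and the plasma counts, and chromatography may remove part of the latter, so the net direction cannot be fixed.

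Finally, retention several hours after injection is not documented. The protocol describes imaging only to 130 min. Holding retention constant as the gap lengthens probably overstates the later rows. This objection stands: steps 2 and 3 show what is possible and do not estimate what will happen.

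**Conclusion.** The contradiction is real, and it bears on the primary analysis. Followed as written, the same-day permission lets residual F-18 enter the ER176 data with no interval, background scan or correction.

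The firm part of the size is physical decay, which needs only the two half-lives and the assumed gap. By that measure F-18 and C-11 are about equal late in a scan of 740 MBq started 3 h after florbetaben. F-18 is about a third of C-11 after 6 h (19/58), and negligible after 24 h. The brain-signal and effect-size figures are illustrative only.

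An upward bias in patients is supported for cortex/cerebellum SUVR alone, and only if both groups are scanned same-day. With unequal exposure, or for V_T/f_P, the direction is open. The number of subjects affected is unknown and may be zero. The matter should be fixed because the correction is cheap and the target comparison has only 15 subjects per group. No sample size or power figure changes.

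**What to change.** Reconcile the conflicting sentences in section 6 with Study Schedule footnotes a and b. State explicitly how 18F-florbetaben is treated, so that residual F-18 cannot enter the ER176 data uncorrected. Which scheduling rule applies is for the sponsor to decide.

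In section 7.2, add that the interval between the florbetaben and ER176 injections is recorded for every subject who has both under this protocol. Any subject given both tracers on one day should be flagged, and the primary effect sizes, for SUVR and for V_T/f_P, reported with and without those subjects, along with the number flagged in each group.

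The cost is a sentence or two of protocol text, one recorded time interval and a small sensitivity analysis. Some subjects may lose a single-day option, depending on how the conflict is resolved. Section 6 already allows for up to five visits.
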